4.5. Subject Number and Identification

Subject numbers will consist of 6 digits in which the first set of 3 digits will identify the site and the second set of 3 digits will identify the subject (eg, 001-101). If subjects are withdrawn by the Investigator (or designee) or voluntarily withdraw prematurely from the study, replacement subjects will be enrolled only if deemed necessary by the Sponsor. If necessary, as determined by the Sponsor, subjects who fail to complete the treatment or have insufficient PK data may be replaced. Replacement subjects will be assigned a subject number by adding 50 to the last 3 digits of the subject number for the subject they are replacing (eg, Subject Number 001-151 replaces Subject Number 001-101).

4.6. Removal of Subjects from Study Participation

Subjects will be informed that they are free to withdraw from the study at any time and for any reason. The Investigator (or designee) may remove a subject from the study if, in the Investigator's (or designee's) opinion, it is not in the best interest of the subject to continue the study. Subjects may be withdrawn because of the following:

- change in compliance with inclusion/exclusion criterion that is clinically relevant and affects subject safety
- occurrence of AEs

- occurrence of pregnancy
- intake of non-permitted concomitant medication that might affect subject safety or study assessments/objectives, etc.

Notification of withdrawal will immediately be made to the Sponsor. In case of withdrawal, efforts will be made to perform all final study day assessments ([Appendix 4](#)). The date the subject is withdrawn from the study and the reason for withdrawal will be recorded on the subject's electronic Case Report Form (eCRF). All withdrawn subjects with AEs that are assessed as related to study drug and which are ongoing at ET may continue to be followed until the symptoms or value(s) return to normal, or acceptable levels, as judged by the Investigator (or designee) and confirmed by the Sponsor.

The entire study may be discontinued at the discretion of the Investigator (or designee) or Sponsor, based on the occurrence of the following:

- AEs unknown to date with respect to their nature, severity, and/or duration;
- increased frequency and/or severity and/or duration of known AEs;
- medical or ethical reasons affecting the continued performance of the study;
- difficulties in the recruitment of subjects;
- cancellation of drug development.

In the event that the study is terminated early, the Sponsor or its designee will provide specific guidance to the CRU regarding the EOS procedures.

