3. INVESTIGATIONAL PLAN

3.1. Overall Study Design and Plan

This is an open-label, single-ascending dose study to evaluate the safety, tolerability, and PK of LOXO-305.

Up to 4 cohorts are planned for evaluation. In each cohort, 6 healthy adult subjects are planned for evaluation. Subjects will participate in only 1 cohort. In each cohort, subjects will receive a single oral dose of LOXO-305 on Day 1. Each cohort will include a sentinel group of 2 subjects will be dosed at least 48 hours before the remaining 4 subjects (following review of all available safety data).

A single oral dose of LOXO-305 will be administered on Day 1 for each cohort as follows:

- Cohort 1 (Treatment A): 300 mg
- Cohort 2 (Treatment B): up to 600 mg
- Cohort 3 (Treatment C): up to 900 mg.

One additional cohort (6 subjects) may be enrolled if it is deemed appropriate to repeat any dose level, or to add an interim dose level or levels (equal to or lower than 900 mg), as determined by the Sponsor in consultation with the Investigator (or designee), depending on the safety, tolerability, and PK results from the prior cohort(s). Dosing will not exceed 900 mg in any subject, nor will any subject be given a dose for which the C_{max} would exceed **CCI** ng/mL.

Dose escalation to a higher dose level (ie, next cohort) will not take place until the Investigator (or designee) and the Sponsor have reviewed all pertinent safety/tolerability data (ie, physical examinations, ECGs, vital sign measurements, clinical laboratory evaluations, and adverse events [AEs]) through a minimum of 168 hours (Day 8) and have determined that adequate safety and tolerability from the previous, lower dose, cohort has been demonstrated to permit proceeding to the next cohort. Pharmacokinetic data through at least 72 hours (approximately 3 half-lives) after dosing will be reviewed to guide the dose-escalation decision. Data from a minimum of 4 subjects will be reviewed in order to make a dose escalation decision. Dose-escalation criteria and stopping rules are described in [Section 5.5](#).

Each treatment (A, B, and C) will be administered orally in the morning following a fast of at least 10 hours prior to and 4 hours after dosing.

The PK sampling will be obtained for 168 hours after administration of each dose of LOXO-305.

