5.5. Dose Escalation Criteria and Stopping Rules

Dose escalation to the next dose level (ie, next cohort) will not take place until the Investigator (or designee) and the Sponsor have determined that adequate safety and tolerability data (ie, physical examinations, ECGs, vital sign measurements, clinical laboratory evaluations, and AEs through 168 hours [Day 8] following dosing on Day 1) from the previous, lower dose, cohort has been demonstrated to permit proceeding to the next cohort. A sufficient period of time will be allowed between dosing (168 hours [Day 8], following dosing on Day 1) of the prior cohort and the dosing of the next cohort in order for the Investigator (or Designee) and the Sponsor to adequately review the safety and tolerability data from the prior cohort. Pharmacokinetic data through at least 72 hours (approximately 3 half-lives) will be reviewed to guide dose-escalation decisions or for selection of an alternate dose for evaluation, and/or to confirm the sampling schedule. Data from a minimum of 4 subjects will be reviewed in order to make a dose escalation decision.

The Investigator (or designee) and the Sponsor will make 1 of the following determinations:

1. To continue with the study as planned.

2. To continue with the study and add additional safety evaluations to subsequent cohorts.
3. In the event of the following occurrence:
 - a. One subject at a given dose level experiences a drug-related Common Terminology Criteria for Adverse Events (CTCAE) grade ≥ 3 toxicity (which is not an SAE), which is deemed clinically significant by the Investigator (or designee), with agreement from the Sponsor, a decision will be made as follows:
 - o Adjust to an intermediate dose between the current dose and the next planned dose;
 - o Adjust to an intermediate dose between the current dose and the previous lower dose;
 - o Dose administration may be permitted to continue as deemed by the Investigator (or designee), with agreement from the Sponsor, where the safety parameter assessed does not pose a subject safety risk based on safety knowledge from prior LOXO-305 studies.
 - b. Two or more subjects in a dose level experience a drug-related CTCAE grade ≥ 3 toxicity (which is not an SAE), which are deemed clinically significant by the Investigator (or designee), with agreement from the Sponsor, a decision will be made as follows:

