7.2.1. Adverse Events

Adverse event definitions; assignment of severity, causality, action taken, and outcome; and procedures for reporting SAEs are detailed in [Appendix 1](#).

Subjects will be asked a non-leading HDYF? question such as “Have there been any changes in your health status since Screening/since you were last asked?” at the timepoints specified in [Appendix 4](#) (ie, at Screening [after the ICF is signed], at Check-in [Day -1], at each postdose vital sign measurement, and at an appropriate time for all other days). Subjects will also be encouraged to voluntarily report AEs occurring at any other time through the EOS.

Adverse events, whether volunteered, identified by the subject's responses to HDYF? inquiries, or noted on physical examination, ECG, vital sign measurements, or clinical laboratory evaluations, will be recorded throughout the study (ie, from signing of the ICF until EOS [or ET if the subject discontinues from the study and does not complete a follow-up phone call]), either as subject medical history (if the event is reported as beginning prior to signing of the ICF or if the event occurs prior to study drug administration on Day 1 and is assessed as not related to study procedures by the Investigator [or designee]) or as AEs (if the event occurs after signing of the ICF but prior to study drug administration on Day 1 and is assessed as related to study procedures by the Investigator [or designee], or if the event occurs after study drug administration on Day 1 through EOT or ET regardless of relationship to study drug). From EOT or ET through EOS, only AEs assessed as related to study drug by the Investigator (or designee) are to be reported. All SAEs that develop from the time of ICF signing until EOS (or ET, if the subject discontinues from the study and does not complete a follow-up phone call) are to be reported.

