8.1.1. Calculation of the Summary Statistics

For continuous data the following rules will be applied:

- Missing values will not be imputed, unless specifically stated otherwise.
- Unrounded data will be used in the calculation of summary statistics.
- If the number of subjects with valid observations ($n < 3$), summary statistics will not be calculated, with the exception of n , minimum, and maximum.
- As ET data is not associated with any scheduled timepoint, it will be excluded from all calculations of summary statistics.
- Postdose repeats and unscheduled assessments will not be included in calculations of summary statistics.

For categorical data the following rules will be applied:

- If the categories of a parameter are ordered (eg, AE severity), all categories between the possible minimum and maximum categories will be included, even if $n = 0$ for a given category. If the categories are not ordered (eg, race), only those categories for which there is at least 1 subject represented will be included.
- Missing values will not be imputed, with the exception of AEs where the 'worst-case' approach will be taken (see [Section 8.6.1](#)), or unless specifically stated otherwise. A 'missing' category will be included for any parameter for which information is missing. This will ensure that the population size totals are consistent across different parameters.

All protocol deviations and data issues (eg missing data, out of protocol window) that occur during the study, including those related to COVID-19, will be considered prior to database lock for their severity/impact on how the data will be displayed.

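### Removal from the study after the only dose (Protocol 4.6) permits all-cause AE reporting and scheduled safety data to stop early in subjects removed for an AE or a non-permitted medication

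*Protocol*

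**What the plan says.** Protocol 3.1 sets a single administration: "In each cohort, subjects will receive a single oral dose of LOXO-305 on Day 1". Section 4.6 then gives a discretionary rule on leaving the study, not on leaving treatment: "The Investigator (or designee) may remove a subject from the study if, in the Investigator's (or designee's) opinion", continuing is not in the subject's best interest. The listed reasons include "occurrence of AEs", with no limit on grade, relatedness or timing, and "intake of non-permitted concomitant medication that might affect subject safety or study assessments/objectives, etc". On withdrawal, the site tries to complete the final-day assessments. Related AEs still ongoing at ET may be followed further.

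Appendix 4 (footnote t) defines ET as release from the unit. On reporting after that, Protocol 7.2.1 says: "From EOT or ET through EOS, only AEs assessed as related to study drug by the Investigator (or designee) are to be reported"; Appendix 4 footnote j repeats the rule. SAEs are reported to End of Study, or only to ET if the follow-up call is not completed. The call, 7 ± 2 days after EOT or ET, asks about SAEs and drug-related AEs only.

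SAP 8.1.1 adds: "As ET data is not associated with any scheduled timepoint, it will be excluded from all calculations of summary statistics". SAP 8.1.2 likewise keeps ET measurements out of calculations, and 8.1.1 does not impute missing continuous values. Protocol 4.5 allows replacement: "subjects who fail to complete the treatment or have insufficient PK data may be replaced".

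**The concern.** In a multiple-dose study, removal for an AE can at least end exposure. Here, once the dose is given, removal ends only observation. The subjects who may be observed less are those who had an AE or took a medicine for one, so missing data can depend on the primary outcome, safety and tolerability. Cohorts have 6 subjects and there is no control group, so one such subject is 1/6 = 17% of a dose level.

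Continued reporting of related AEs is a weak substitute for all-cause reporting. Appendix 1 calls an AE related only if no other cause can be identified, and names concomitant drugs as an example of such a cause. A subject removed for taking a medication already has a candidate other cause. Such an event, if its timing fits the drug, does not clearly meet the not-related definition either, because that requires the time course to rule causality out. Whether it is reported after ET therefore rests on a judgement that the definitions do not settle.

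**Working it through.** The documents give no figure for this point, so there is none to reproduce. The check follows one illustrative subject, with ET just after the 24 h assessments on Day 2, and compares that subject with a completer.

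**AE window.** All-cause reporting runs to EOT or ET.
- Completer: 168 h (Day 8). Removed subject: 24 h, so 168 − 24 = 144 h, or 6 days, are lost.
- Follow-up call: Day 8 + 7 = Day 15 ± 2 for the completer; Day 2 + 7 = Day 9 ± 2 for the removed subject. The SAE window shortens by the same 6 days.

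**Scheduled safety data** (Appendix 4 grid and footnotes e, f, u).
- Post-dose vital signs: 45 min and 2, 4, 24, 48, 72, 96, 120, 144 and 168 h, which is 10 times. Not done: 6 of 10 after ET at 24 h; 7 of 10 if ET is just after 4 h; 4 of 10 if just after 72 h.
- Post-dose ECGs: 2 h, 4 h, Day 2, Day 4 and Day 8. The last two are not done on schedule.
- Post-dose laboratory panels: Day 4 (read from the grid) and Day 7 (footnote u). Neither is done. The ET panel is taken on the day of release but is excluded from summaries, so this subject contributes no post-dose laboratory value to the by-timepoint tables.

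**PK.** Inputs: tmax about 2 h and half-life about 20 h (Protocol 1.3.2, patients); a half-life of 24 h is implied by equating 72 h with about 3 half-lives (72/3 = 24). A one-compartment oral model is assumed. With ke = ln2/t½, and ka chosen so that ln(ka/ke)/(ka − ke) = 2 h, the fraction of AUC0-inf beyond T, once absorption is complete, is f(T) = exp(−ke·T)/(1 − ke/ka).

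| | t½ 20 h | t½ 24 h |
|---|---|---|
| ke; ka (per h) | 0.0347; 2.08 | 0.0289; 2.19 |
| f(24 h) | 0.435/0.983 = 44% | 0.500/0.987 = 51% |
| f(48 h) | 19% | 25% |
| f(72 h) | 8% | 13% |
| f(168 h) | 0.3% | 0.8% |
| T at which f = 30% | 35 h | 42 h |

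SAP 8.5.1.2 allows AUC0-inf and derived parameters to be excluded when extrapolation exceeds 30%. Under these assumptions that happens if sampling stops before about 35 to 42 h. Cmax and AUC0-24 survive if ET falls after 24 h.

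**The case against.** Much of the opposing case stands.

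- Removal is optional and tied to the subject's best interest. The 4.6 list also serves the period from check-in to dosing, so it is not pointless in a single-dose study.
- The medication reason is narrow. Protocol 6.1 accepts acetaminophen within limits, and the investigator and sponsor may approve other medicines.
- The triggering AE is recorded, with the reason for withdrawal. The subject stays in the safety population, and SAP 8.6.1 has rows for TEAEs leading to discontinuation. Related AEs and SAEs are still sought at the call, and ET values are listed.
- The PK loss is conditional. The 30% rule is discretionary, SAP 8.5.1.2 allows another AUC measure, and early vomiting may exclude a subject from the PK analysis in any case. The PK rows of Appendix 4 are redacted, so a sample at ET cannot be ruled out, though one sample would not replace a terminal profile.

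A reader might infer that escalation could rest on unaffected subjects, because "Data from a minimum of 4 subjects will be reviewed in order to make a dose escalation decision". The documents do not support this. Four is a floor, not a filter: the review covers all pertinent safety data, and the 5.5 criteria count events in any subject at a dose level, withdrawn or not.

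What remains unanswered is the shorter all-cause AE window and the gap in the by-timepoint summaries. Neither the listings nor the discontinuation rows restore events that were never collected.

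**Conclusion.** The point holds in limited form. For a dosed subject removed under 4.6, the plan's own rules end all-cause AE reporting at ET and leave later scheduled safety results out of the summaries. For removal just after 24 h, that costs 6 of 7 days of all-cause AE reporting, 6 of 10 post-dose vital-sign times, and both scheduled post-dose laboratory panels. The effect on AUC0-inf, CL/F and Vz/F is secondary and matters mainly for ET before about 35 to 42 h. It rests on the assumed model and on a half-life estimated in patients.

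The documents give no basis for the frequency of such removals; the loss is permitted, not certain. A reader might also infer that each dose will look generally better tolerated than it was. The documents do not show that: the triggering event, related AEs and SAEs remain in the record, and the subject remains in the denominator. What is at risk is later non-serious events judged unrelated, and the completeness of the laboratory, ECG and vital-sign summaries. The change is worth making because it bears on the primary objective and costs little.

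**What to change.** 1. Amend Protocol 7.2.1, the content of the follow-up call and Appendix 4 footnote j, so that AEs regardless of relationship are collected through nominal Day 8 for every dosed subject who can be reached, including ET subjects.
2. Reconcile 4.6 with the single-dose design by separating removal before dosing from events after dosing. State that a dosed subject who meets a 4.6 reason continues scheduled safety and PK data collection through Day 8 where the subject consents and the investigator has no safety objection. Judge the effect of any medication on PK under SAP 7.3. Removal and clinical care remain the investigator's decision, and the right to withdraw is unchanged.
3. In the SAP, before database lock, report ET safety values and each withdrawn subject's AE observation time alongside the by-timepoint summaries.

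The cost is a short protocol amendment and a small SAP change. Confinement to Day 8 is already planned, so no subjects or scheduled visits are added. A few subjects would stay, or be contacted, who would otherwise have been released. If enrolment is complete, item 3 can still be done.

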5. STUDY TREATMENTS

5.1. Description, Storage, Packaging, and Labeling

The Sponsor (or designee) will provide the Investigator (or designee) with adequate quantities of the LOXO-305.

Table 3 Study Drugs

Study Drug	LOXO-305
Form^a	Tablet
Strength	25 mg
Supplier	Loxo Oncology, Inc.
Manufacturer	Bend Research, Inc.

^a Specific ingredients/purity will be identified in the Certificate of Analysis (or equivalent) that is supplied with the study drug(s).

The tablets containing 25 mg LOXO-305 will be supplied by the Sponsor (or designee), along with the batch/lot numbers and Certificate of Analysis. It will be provided in high-density polyethylene bottles and stored according to the instructions on the label.

Size 0 light blue opaque capsules to over-encapsulate LOXO-305 tablets will be supplied by Covance. LOXO-305 tablets will be over-encapsulated (with 4 tablets of LOXO-305 being placed in each capsule) according to Covance CRUs Standard Operating Procedures (SOPs) and relevant processes.

Study drugs will be stored at the CRU in a location that is locked with restricted access.

The bulk drug container and unit dose containers will be labeled in accordance with national laws and regulations. The study drug will be transferred from bulk supplies into the subject's dose container by qualified CRU employees. Each unit dose container will be appropriately labeled.

5.2. Study Treatment Administration

Cohort 1 (Treatment A):

- A single oral dose of 300 mg LOXO-305 (12 × 25-mg tablets, over-encapsulated [3 capsules]) following a fast of at least 10 hours prior to and 4 hours after dosing.

Cohort 2 (Treatment B):

- A single oral dose of up to 600 mg LOXO-305 (24 × 25-mg tablets, over-encapsulated [6 capsules], or less depending on the dose chosen) following a fast of at least 10 hours prior to and 4 hours after dosing.

Cohort 3 (Treatment C):

- A single oral dose of up to 900 mg LOXO-305 (36 × 25-mg tablets, over-encapsulated [9 capsules], or less depending on the dose chosen) following a fast of at least 10 hours prior to and 4 hours after dosing.

One additional cohort (6 subjects) may be enrolled if it is deemed appropriate to repeat any dose level, or to add an interim dose level or levels (equal to or lower than 900 mg), as determined by the Sponsor in consultation with the Investigator (or designee), depending on the safety, tolerability, and PK results from the prior cohort(s). Dosing will not exceed 900 mg in any subject, nor will any subject be given a dose for which the C_{max} would exceed **CC1** ng/mL.

All study drugs will be administered with approximately 240 mL of water. An additional 240 mL of water may be administered if needed.

Each unit dose will be prepared by qualified CRU staff. Each unit dose container will be appropriately labelled.

Appropriate unit dose(s), as described above, will be administered to subjects. Although the timing of events requires that each subject will be consistently administered the appropriate dose at a specific time, the exact dose time of subjects may be staggered to obviate the need to have all subjects on precisely the same study schedule. For each dose, the subject's actual dose time will be recorded in the source documents and transcribed into the eCRF.

Subjects will be instructed not to crush, split, or chew the study drugs.

Subjects will not lay supine for 4 hours following LOXO-305 dose administration, except as necessitated by the occurrence of an AE(s) and/or study procedure(s).

5.3. Randomization

This is a nonrandomized study.

5.4. Blinding

This is an open-label study.

5.5. Dose Escalation Criteria and Stopping Rules

Dose escalation to the next dose level (ie, next cohort) will not take place until the Investigator (or designee) and the Sponsor have determined that adequate safety and tolerability data (ie, physical examinations, ECGs, vital sign measurements, clinical laboratory evaluations, and AEs through 168 hours [Day 8] following dosing on Day 1) from the previous, lower dose, cohort has been demonstrated to permit proceeding to the next cohort. A sufficient period of time will be allowed between dosing (168 hours [Day 8], following dosing on Day 1) of the prior cohort and the dosing of the next cohort in order for the Investigator (or Designee) and the Sponsor to adequately review the safety and tolerability data from the prior cohort. Pharmacokinetic data through at least 72 hours (approximately 3 half-lives) will be reviewed to guide dose-escalation decisions or for selection of an alternate dose for evaluation, and/or to confirm the sampling schedule. Data from a minimum of 4 subjects will be reviewed in order to make a dose escalation decision.

The Investigator (or designee) and the Sponsor will make 1 of the following determinations:

1. To continue with the study as planned.

2. To continue with the study and add additional safety evaluations to subsequent cohorts.
3. In the event of the following occurrence:
 - a. One subject at a given dose level experiences a drug-related Common Terminology Criteria for Adverse Events (CTCAE) grade ≥ 3 toxicity (which is not an SAE), which is deemed clinically significant by the Investigator (or designee), with agreement from the Sponsor, a decision will be made as follows:
 - o Adjust to an intermediate dose between the current dose and the next planned dose;
 - o Adjust to an intermediate dose between the current dose and the previous lower dose;
 - o Dose administration may be permitted to continue as deemed by the Investigator (or designee), with agreement from the Sponsor, where the safety parameter assessed does not pose a subject safety risk based on safety knowledge from prior LOXO-305 studies.
 - b. Two or more subjects in a dose level experience a drug-related CTCAE grade ≥ 3 toxicity (which is not an SAE), which are deemed clinically significant by the Investigator (or designee), with agreement from the Sponsor, a decision will be made as follows:
 - o Dose administration may be permitted to continue as planned if deemed acceptable by the Investigator (or designee), with agreement from the Sponsor, where the safety parameter assessed does not pose a subject safety risk based on safety knowledge from prior LOXO-305 studies;
 - o Evaluate an alternative dose level;
 - o The study may be terminated with no additional dose administration to any subjects.
 - c. One or more subject(s) in a dose level has a C_{max} of $> \text{CCI}$ ng/mL or a predicted C_{max} of $\geq \text{CCI}$ ng/mL in a subsequent dose level, a decision will be made as follows:
 - o Adjust to an intermediate dose between the current dose and the previous lower dose;
 - o The study may be terminated with no additional dose administration to any subjects.

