Protocol Medical Writer	PPD [REDACTED] Covance Tel: PPD [REDACTED] Email: PPD [REDACTED]

SYNOPSIS

Study Title

A Phase I, Single-Ascending Dose Study to Evaluate the Safety, Tolerability, and Pharmacokinetics of LOXO-305 in Healthy Adult Subjects

Objectives

The primary objective of the study is:

- To assess the safety and tolerability of single oral doses of LOXO-305 when administered to healthy adult subjects.

The secondary objective of the study is:

- To assess the pharmacokinetics (PK) of single oral doses of LOXO-305 when administered to healthy adult subjects.

Study Design

This is an open-label, single-ascending dose study to evaluate the safety, tolerability, and PK of LOXO-305.

Up to 4 cohorts are planned for evaluation. In each cohort, 6 healthy adult subjects are planned for evaluation. Subjects will participate in only 1 cohort. In each cohort, subjects will receive a single oral dose of LOXO-305 on Day 1. In each cohort, a sentinel group of 2 subjects will be dosed at least 48 hours before the remaining 4 subjects in the cohort (following review of available safety data). Blood samples will be collected for the PK assessment of LOXO-305 in plasma for 168 hours postdose.

A single oral dose of LOXO-305 will be administered on Day 1 for each cohort as follows:

- Cohort 1 (Treatment A): 300 mg
- Cohort 2 (Treatment B): up to 600 mg
- Cohort 3 (Treatment C): up to 900 mg

One additional cohort (6 subjects) may be enrolled if it is deemed appropriate to repeat any dose level, or to add an interim dose level or levels (equal to or lower than 900 mg), as determined by the Sponsor in consultation with the Investigator (or designee), depending on the safety, tolerability, and PK results from the prior cohort(s). Dosing will not exceed 900 mg in any subject, nor will any subject be given a dose for which the maximum observed plasma concentration (C_{max}) would exceed **CCI** ng/mL.

Dose escalation to a higher dose level (ie, next cohort) will not take place until the Investigator (or designee) and the Sponsor have reviewed all pertinent safety/tolerability data (ie, physical examinations, electrocardiograms [ECGs], vital sign measurements, clinical laboratory evaluations, and adverse events [AEs]) through a minimum of 168 hours (Day 8) and have determined that adequate safety and tolerability from the previous lower dose

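### Protocol Section 5.5 has no criterion for a drug-related serious adverse event, so the most serious drug-related events fall outside its predefined stopping rules

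*Protocol*

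**What the plan says.** Protocol Section 5.5 states that "The Investigator (or designee) and the Sponsor will make 1 of the following determinations" and then lists three items. Item 1 is to go on as planned. Item 2 is "To continue with the study and add additional safety evaluations to subsequent cohorts". Item 3 names three occurrences and the responses to each:

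- **3a**: one subject at a dose level with drug-related CTCAE grade 3 or higher "toxicity (which is not an SAE), which is deemed clinically significant by the Investigator (or designee), with agreement from the Sponsor". The responses are two kinds of dose adjustment, or conditional continuation.
- **3b**: two or more subjects with drug-related grade 3 or higher "toxicity (which is not an SAE), which are deemed clinically significant by the Investigator (or designee), with agreement from the Sponsor". One response is that "Dose administration may be permitted to continue as planned if deemed acceptable by the Investigator (or designee), with agreement from the Sponsor", again with a condition. The others are a different dose level or possible termination.
- **3c**: "One or more subject(s) in a dose level has a" Cmax above a limit, or the Cmax predicted for a later level reaches one (both limits are redacted). The responses are a lower intermediate dose or possible termination.

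The sentinel arrangement is in the Synopsis and Section 3.1. In the wording of 3.1, 2 subjects are "dosed at least 48 hours before the remaining 4 subjects (following review of all available safety data". The Synopsis has almost the same sentence.

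Four other provisions bear on the point:

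- The opening of 5.5 makes escalation wait until the Investigator and Sponsor find the previous cohort's safety adequate. That uses safety data through 168 hours and data from at least 4 subjects.
- Appendix 1 requires notification of any SAE within 24 hours.
- Section 4.6 lets the Investigator or the Sponsor discontinue the whole study, for reasons that include AEs of a previously unknown nature, severity or duration.
- SAP Section 4 restates the design and adds no stopping rule.

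**The concern.** The exclusion of SAEs from 3a and 3b has no counterpart that picks them up. One non-serious grade 3 event judged clinically significant leads to a joint decision with listed responses. One Cmax excursion leads to a lower dose or possible termination, with no continue option listed. A drug-related life-threatening event leads to nothing predefined. The rules are therefore silent where one would most expect them to speak.

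The subjects are healthy volunteers who receive no health benefit (Section 1.5). Earlier healthy-volunteer doses were 200 mg and the highest patient dose was 300 mg once daily (Sections 1.3 and 1.5), while this study may reach 900 mg. Section 3.3 says that PK linearity above 300 mg is unknown, and Section 1.2 reports a steep dose response for toxicity in the 28-day dog study. Section 1.5 relies on the escalation procedures and safety monitoring to protect subjects. At stake is whether further volunteers could be dosed at the same level after a drug-related SAE without a required pause, joint agreement or a record of the reasons.

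**Working it through.** The documents give no figure to reproduce, and no event rate is assumed. The check is a comparison of texts.

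1. **Do the item 3 triggers cover a drug-related SAE?** 3a: no, SAEs are excluded in terms. 3b: no, the same exclusion. 3c: no, it concerns Cmax and not a clinical event. Result: 0 of 3. The only redactions visible in the list are Cmax values, so they do not hide an SAE rule.

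2. **What does the exclusion remove?** Set the severity grades in Appendix 1 beside its SAE definition:
   - Grade 5 is death; death is an SAE outcome.
   - Grade 4 is immediate risk of death; a life-threatening experience is an SAE outcome.
   - Grade 3 includes events for which hospitalization is indicated; inpatient hospitalization is an SAE outcome.

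   On that wording, only grade 3 events without an SAE outcome clearly remain countable under 3a and 3b.

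3. **Does any other provision require same-level dosing to be held because of the SAE?**
   - Review before the rest of the cohort is dosed: mandatory, but it names neither a reviewer nor a finding that would hold the remaining subjects.
   - Adequate-safety condition in 5.5: binding and joint, but it governs the move to the next cohort. Its minimums of 168 hours and 4 subjects show that it was not written for the step from 2 sentinels to the rest.
   - SAE notification: timed, with no dosing consequence attached.
   - Section 4.6: permissive, does not name SAEs, and concerns ending the whole study, not pausing a dose level.

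   Result: none does.

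4. **How many subjects does one sentinel event bear on?** Cohort size minus sentinels = 6 − 2 = 4, all at the same dose level.

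**The case against.** The strongest reply is that the list in 5.5 should not be read alone. Continuing as planned still includes the adequate-safety condition before escalation. Cohorts 2 and 3 are set at up to 600 mg and up to 900 mg, and the optional cohort may repeat a level or add an interim one, so the dose can be changed without any item 3 trigger. Section 4.6 lets either party stop the study, and a drug-related SAE would plausibly qualify: the healthy-volunteer events reported so far are three grade 1 events in one subject. The exclusion may even be protective, because it withholds from SAEs the express permission to continue that 3a and 3b give.

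Much of this stands, and it rules out three stronger readings that a reader might infer:

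- **That after an SAE the team may only continue, since items 1 and 2 are what remains in the list.** The escalation condition, the dose flexibility and Section 4.6 all allow otherwise.
- **That every non-sentinel subject in the study is exposed to the gap at once.** One sentinel event concerns at most the 4 others in that cohort.
- **That an SAE could go unnoticed until after the rest are dosed, because the 24-hour notification period may run past the 48-hour minimum.** Subjects are confined to the unit, 48 hours is a minimum, and a safety review must come first.

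What the reply does not supply is a provision that holds same-level dosing because a drug-related SAE occurred. The protective reading of the exclusion is an inference that the text does not state.

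**Conclusion.** The point holds as a gap in a stated stopping rule. Section 5.5 predefines a joint decision for lesser toxicity and for Cmax but not for a drug-related SAE, and no text in either document requires a hold after one. The existing safeguards would probably produce a pause, but by judgement and not by rule. They do not require the Investigator and Sponsor to agree on resuming at the same level, or to document why. The size is up to 4 further subjects per sentinel event.

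The conclusion rests on Appendix 1's own wording of the grades and of an SAE. It does not depend on the redacted Cmax limits. The change should be made; the safeguards already in place keep the gap from being a critical failing.

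**What to change.** Add item 3d to Section 5.5. If any subject has a drug-related SAE, no further subject is dosed at that dose level or higher, including the remaining 4 of a cohort after the sentinel pair, until the Investigator (or designee) and Sponsor have completed and documented a safety review. The outcomes are a lower or intermediate dose, termination, or continuation with a documented rationale. State that the 168-hour and 4-subject minimums do not apply to this hold. In the Synopsis and Section 3.1, refer to 3d in the sentinel sentence.

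Do not extend 3a and 3b to the sentinel step. That goes beyond the SAE gap. Their dose adjustments could also split a cohort into 2 and 4, leaving 2 subjects at the sentinel dose, below the minimum of 4 for an escalation decision.

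The drafting cost is one item and two cross-references, with no added scheduled visits or samples. The operating cost is delay, and only if a drug-related SAE occurs. If the review changes the dose part-way through a cohort, the same 2-and-4 split can arise and the cohort may need completing or repeating. SAP Section 10 already assigns four dose levels, which at 6 subjects each use all 24 planned subjects (4 × 6 = 24), so that could mean extra subjects. In Cohort 1 a lower dose would fall below the 300 mg floor of the primary endpoint in Section 2.2.1. Item 3d still relies on the Investigator's assessment of relatedness and still permits continuation. What it adds is a required pause, joint agreement and a record.
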